7.3.3.3 Week 3 (Day 15 ± 3 Day)

- Adverse events
- Concomitant medications
- Hematology weekly as needed (see above)
- Blood chemistry weekly as needed (see above)

7.3.3.4 Week 4 (Day 22 ± 3 Day) (Rest Period)

- Adverse events
- Concomitant medications
- Hematology weekly as needed (see above)
- Blood chemistry weekly as needed (see above)

7.3.4 End of Odd Numbered Cycles Up to Month 12

- Response assessment, based on peripheral blood

7.3.5 End of Even Numbered Cycles Up to and Including Month 12

- Bone marrow sample for response assessment
- Bone marrow aspirate and biopsy core for exploratory objectives. If no aspirate is available, then peripheral blood is acceptable.

7.3.6 After Month 12

Every 3 Month Visits:

- Adverse events
- Concomitant medications
- Bone marrow aspirate and biopsy / response assessment
- Bone marrow aspirate and biopsy core for exploratory objectives. If no aspirate is available, then peripheral blood is acceptable.
- CBCs as needed.

7.4 Control Arm (azacitidine)

In the event that a visit or test cannot be scheduled on the exact visit day, a window of ±3 days is allowable. After the first cycle, Day 1 of each subsequent cycle is the same as Day 29 of the previous cycle.

7.4.1 Each Cycle Day 1 \pm 3 Days (same as Day 29 of previous cycle) through Day 10

Tests should be performed prior to first dose

Day 1 examinations marked * do not need to be repeated if already performed within 3 days prior to day 1 cycle 1.

- Adverse Events: All adverse events since the last visit should be recorded. Even though pre-medicated, patients should be closely monitored.
- Concomitant medications.
- Physical examination: Day 1*. Weight, body surface area.
- ECOG performance status: Day 1.
- Vital signs. **If azacitidine is given IV:** before (within 0-2 hours) and EOI (30-60 minutes). **If azacitidine is given SC: before administration (within 0-2 hours).**
- Hematology: Day 1* hemoglobin, hematocrit, MCV, platelet count, blasts, WBC and WBC differentials.
- Blood chemistry: Day 1* sodium, potassium, BUN, glucose, ALT/AST, alkaline phosphatase, total protein, total bilirubin, albumin, creatinine, calcium, chloride and magnesium.
- Azacitidine will be administered daily for 7 consecutive days starting on Day 4 (Days 4 to 10 inclusive). SC preferred but will allow for IV at the discretion of the treating physician. If SC (or IV) is used on Day 4, the other days should follow the same method of administration.
- Pharmacokinetics for azacitidine: Only Cycle 1 Day 4, per Section 8.3.

7.4.2 Perform Weekly

- Adverse events
- Concomitant medications
- Hematology
- Blood chemistry

7.4.3 End of Odd Numbered Cycles Up to Month 12

- Response assessment, based on peripheral blood

7.4.4 End of Even Numbered Cycles Up to and Including Month 12

- Bone marrow sample for response assessment
- Bone marrow aspirate and biopsy core for exploratory objectives. If no aspirate is available, then peripheral blood is acceptable.

7.4.5 After Month 12

Every 3 Month Visits:

- Adverse events
- Concomitant medications
- Bone marrow aspirate and biopsy / Response assessment
- Bone marrow aspirate and biopsy core for exploratory objectives. If no aspirate is available, then peripheral blood is acceptable.
- CBCs as needed.

7.5 End of Treatment Visit (All Patients)

This visit should take place within 28 days of the last dose of APR-246 or azacitidine, if treatment is stopped early for any reasons.

- Physical examination: weight, body surface area.
- Vital Signs
- Disease Assessment
- Bone marrow aspirate and biopsy core for exploratory objectives. If no aspirate is available, then peripheral blood is acceptable.
- ECOG performance status
- Hematology
- Blood chemistry
- Safety: Adverse events must be collected up to 30 days after the last dose.

7.6 Long-Term Follow-Up

This can be done remotely (e.g. via telephone, via General Practitioner or via review of medical records).

Assuming there is no withdrawal of consent, patients who stop study treatment (APR-246 or azacitidine) for any reason (e.g. toxicity, transition to SCT, PD) will continue long-term follow-up:

1. Patients who discontinue study treatment to receive SCT:
 - a. Collect post SCT response assessments, transformation to AML and survival every month until relapse or death, whichever occurs first.
 - b. After PD, collect data for survival and transformation to AML every 6 months until death.
2. Responders (CR, PR, mCR with HI, mCR without HI, HI) who discontinue study treatment for other reasons than progressive disease or SCT:
 - a. Collect response assessments, transformation to AML and survival monthly until relapse or death, whichever occurs first.

- b. After relapse/progression, continue collecting data for survival and transformation to AML every 6 months until death.
3. Non-Responders: patients who discontinue study treatment due to progressive disease:
 - a. Collect data for survival and transformation to AML every 6 months until death.

8.0 STUDY ASSESSMENTS

8.1 Safety Assessments

All randomized patients who received any amount of study medication will be evaluated for safety. Adverse events (AEs) are collected during the study, from the time of eligibility confirmation, until 30 days after the last dose of study treatment. AEs are graded according to NCI CTCAE version 5.0. Patients will be assessed at baseline and throughout the study according to the Schedule of Study Evaluations including AEs, laboratory abnormalities, vital signs, physical exam, ECG and performance status.

8.1.1 Safety Analysis

Safety data including AEs, vital signs, laboratory data, ECG, and physical exam will be tabulated for the safety population. Adverse events will be tabulated by body system, preferred term, severity, and relationship to treatments. The tabulation of laboratory parameters will include the normal ranges for each parameter. Each value will be classified as falling above, below, or within the normal range. Laboratory parameters will also be tabulated by maximum NCI-CTCAE severity grade.

8.1.2 Reporting of Adverse Events

8.1.2.1 Adverse Events

An adverse event (AE) is any untoward medical occurrence in a patient or clinical investigation subject administered a pharmaceutical product that does not necessarily have a causal relationship with the treatment. An adverse event includes abnormal laboratory values or test results, even when they do not induce clinical signs or symptoms or require therapy.

The adverse event reporting period begins at the time of eligibility confirmation and will continue up to 30 days after the last dose of study treatment.

At each evaluation patients should be interviewed in a non-directed manner to elicit potential adverse reactions from the patient. The occurrence of an adverse event will be based on changes in the patient's physical examination, laboratory results, and/or signs and symptoms.

All adverse events (except Grade 1 and 2 laboratory abnormalities that do not require an intervention), regardless of causal relationship, are to be recorded in the case report form and source documentation. Adverse events are to be coded according to MedDRA version 21.1. The Investigator must determine the intensity of any adverse events according to the NCI Common Terminology Criteria for Adverse Events (CTCAE) Version 5.0 (see

<http://ctep.info.nih.gov>) and their causal relationship. Those AEs not covered by these criteria will be graded as follows:

1. Mild: Discomfort noticed, but no disruption of normal daily activity. Prescription drug not ordinarily needed for relief of symptom but may be given because of personality of patient.
2. Moderate: Discomfort sufficient to reduce or affect normal daily activity. Patient is able to continue in study; treatment for symptom may be needed.
3. Severe: Incapacitating, severe discomfort with inability to work or to perform normal daily activity. Severity may cause cessation of treatment with test drug; treatment for symptom may be given and/or patient hospitalized.
4. Life-Threatening: Symptom(s) place the patient at immediate risk of death from the reaction as it occurred; it does not include a reaction that, had it occurred in a more serious form, might have caused death.
5. Fatal: Event caused the death of the patient.

Adverse events will be followed until resolution or stabilization while the patient remains on-study. Once the patient is removed from study, events thought to be related to the study medication will be followed until resolution or stabilization, unless, in the Investigator's opinion the event is unlikely to resolve due to the patient's underlying disease, or until the patient starts a new treatment.

Laboratory values are to be graded based on the NCI-CTCAE version 5.0 criteria.

8.1.2.2 Attribution Definitions

An adverse event is considered to be associated with the use of the Investigational agent if the attribution is determined as possible, probable or definite. Attribution of AEs will be recorded in the CRF as:

- Unrelated: The AE is clearly not related to the study treatment.
- Unlikely: The AE is doubtfully related to the study treatment.
- Possible: The AE may be related to the study treatment.
- Probable: The AE is likely related to the study treatment.
- Definite: The AE is clearly related to the study treatment.

8.1.2.3 Definition of an Unexpected Adverse Event

An unexpected adverse event is defined as any adverse drug experience, the specificity or severity of which is not consistent with the current IB; or, if an IB is not required or available, the specificity or severity of which is not consistent with the risk information described in this protocol or in the regulatory agency study authorization application.

Unexpected, as used in this definition, refers to an adverse drug experience that has not been previously observed (e.g., included in the IB) rather than from the perspective of such experience not being anticipated from the pharmacological properties of the pharmaceutical product.

8.1.2.4 Serious Adverse Event (SAE)

A serious adverse event is defined as any untoward medical occurrence that at any dose:

1. Results in death,
2. Is life-threatening (i.e., the patient was at risk of death at the time of the event. It does not refer to an event which hypothetically might have caused death if it was more severe),
3. Requires in-patient hospitalization or prolongation of existing hospitalization excluding that for pain management, disease staging/re-staging procedures, or catheter placement unless associated with other serious events,
4. Results in persistent or significant disability/incapacity, or
5. Is a congenital anomaly/birth defect.

Important medical events that may not result in death, be life-threatening, or require hospitalization may be considered serious adverse drug events when, based on appropriate medical judgment, they may jeopardize the patient or subject and may require medical or surgical intervention to prevent one of the outcomes listed above.

8.1.2.5 Pregnancy

Any pregnancy diagnosed during the study, or that occurs within 30 days after stopping study medication, must be reported immediately to the Investigator. Pregnancy, in and of itself, is not regarded as an adverse event, unless there is suspicion that study medication may have interfered with the effectiveness of a contraceptive medication. If the patient becomes pregnant while on-study, the study drug should be immediately discontinued. Pregnancy information about a female patient or a female partner of a male patient should be reported immediately from the time the Investigator first becomes aware of a

pregnancy or its outcome. This will be performed by the Investigator completing a Pregnancy Form and forwarding it to Theradex Oncology fax number at **REDACTED**
REDACTED

Any pregnancy complication, spontaneous abortion, elective termination of a pregnancy for medical reasons, outcome of stillbirth, congenital anomaly/birth defect, or serious adverse event in the mother will be recorded as an SAE and will be reported as described in Section 8.1.2.6.

8.1.2.6 Reporting of Serious Adverse Events

Adverse events classified as serious require expeditious handling and reporting to Theradex Oncology to comply with regulatory requirements.

All SAEs, regardless of relationship to the study drug, which occur during the period of observation (from the time of eligibility confirmation to 30 days following the date of the last dose of study drug administration) must be immediately reported (within 1 business day of the initial observation of the event) by email, fax or telephone to the Theradex Oncology Safety Desk. Notification by email is preferred. After this period, only those SAEs assessed as possibly, probably or definitely related to the study drug should be reported.

SAEs will be reported to: Theradex Oncology Safety Desk

REDACTED

8.1.2.7 Safety Monitoring Plan

The medical monitor will be responsible for ongoing safety monitoring for the study per the detailed safety plan. This monitoring will include a review of all serious adverse events as they are reported by the study site. The medical monitor will also be in contact with site monitors and will be available to discuss any issues concerning safety with site staff. Safety data will be reviewed periodically by Theradex Medical Monitor and the Sponsor Medical Officer.

8.1.3 Independent Data Monitoring Committee (IDMC)

The Independent Data Monitoring Committee (IDMC) will be formed to, at pre-specified data-points, review and evaluate the study progress and safety, and to assess reports on cumulated serious adverse events (SAEs). Based on these reviews the IDMC will provide recommendations to the sponsor Aprea regarding the scientific and ethical integrity, the progress and possible modifications of the study.

8.2 Efficacy Assessments

The primary endpoint is CR per the modified IWG (Cheson et al, 2006; see [Appendix II](#)) and time between achieving CR and relapse of disease.

8.2.1 Duration of Response

Duration of response (DOR) is measured from the time of initial response to disease **relapse**/progression or death.

8.2.2 Overall Survival

Overall survival is defined for all randomized patients, as measured from the date of randomization until the date of death.

8.2.3 Stem Cell Transplant

Patients may go on to receive SCT and this is likely to be a reflection of a positive outcome to treatment with the randomized therapies. The primary approach will be to use a treatment policy strategy (ICH E9 (R1) addendum)³³ where patients who receive SCT will continue to be followed for OS and relapse from any response with their date of death/relapse used in the analysis. If for any reason a patient receives SCT prior to a documented CR they will not be counted as a response. The inverse probability of censoring weights (IPCW)³⁴ method will be used adjusting for baseline predictors of outcome and time-dependent covariates such as blast, platelet and neutrophil counts. For patients who receive SCT, this method effectively replaces their outcome with patients who most resemble them and who do not receive SCT, in terms of response treatment and baseline attributes. The IPCW approach is preferred to censoring patients who receive SCT, as receipt of SCT is associated with a good response to therapy and would introduce informative censoring and underestimate the true DOR.

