	
APR-246 + azacitidine treatment vs. azacitidine only. Secondary Objectives: To measure the following with APR-246 + azacitidine treatment vs. azacitidine alone:
 
 1. Overall response rate (ORR) 2. Duration of response (DOR) 3. Rate and time to acute myeloid leukemia (AML) transformation 4. Overall survival (OS) 5. Relapse-free survival (RFS) 6. Transition rate to hematopoietic stem cell transplant (HSCT) 7. Safety profile 8. Rate of red blood cell (RBC) and/or platelet transfusion independence (TI) for 56 days (8 weeks) 9. Pharmacokinetics of APR-246 and azacitidine 
Exploratory Objectives:
 
 1. Determine if biomarkers predictive for response to therapy can be derived from baseline molecular analyses of bone marrow or blood samples 2. Determine the depth of remission by IHC, PCR, and other techniques in serial bone marrow or blood samples 3. Investigate potential resistance mechanisms by molecular analysis of bone marrow or blood samples at disease progression 
VAF

Study Endpoints
	
Primary Endpoint: CR per the modified IWG (Cheson et al, 2006)¹ and time between achieving CR and relapse of disease. Secondary Endpoints:
 
 1. ORR is the proportion of patients achieving hematological improvement (HI), partial remission (PR), CR, marrow CR by the IWG 2006 criteria 2. Response duration 3. AML transformation according to World Health Organization (WHO) criteria 4. OS 5. RFS 6. Proportion of patients who transition to HSCT 7. Safety endpoints can relate to adverse events, serious adverse events, dose adjustments or dose holds, lab parameter values, vital signs, ECGs 8. Patients who achieve RBC and/or platelet TI during the 56-day (8 week) period after randomization 9. Pharmacokinetic endpoints: C_{max} (maximum concentration), AUC (area under the curve), Vd and clearance (CL) of APR-246 and azacitidine 
Exploratory Endpoints:
 
 1. Baseline molecular analyses may include, but are not limited to: TP53 VAF by NGS, p53 immunohistochemistry, mutations in other genes by NGS, RNA expression 2. Investigations of depth of remission may include, but are not limited to: PCR and p53 immunohistochemistry 3. Molecular analyses at disease progression may include, but are not limited to: TP53 VAF by NGS, p53 immunohistochemistry, mutations in other genes by NGS, RNA expression

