4.0 TRIAL DESIGN

4.1 Overview of Trial Design

This will be a Phase III, multicenter, randomized study to compare the rate of CR and duration of CR, in patients with *TP53*-mutated MDS who will receive APR-246 and azacitidine or azacitidine alone.

Treatment will be administered on an outpatient basis. No investigational or commercial agents or therapies other than those described below may be administered with the intent to treat the patient's disease.

Patients will be randomized (1:1) to one of two arms, stratified by age (< 65 years versus ≥ 65):

1. Experimental arm: APR-246 + azacitidine; or
2. Control arm: Azacitidine

The ITT population will be the primary analysis population for efficacy. All patients who are randomized on study will be considered eligible for the ITT population and will be used for demographics, baseline characteristics summaries.

Patients may continue treatment to the end of the trial as long as toxicity remains acceptable, progression has not occurred and the patient has not withdrawn consent. Response and progressive disease will be assessed based on the Guidelines for Implementation of International Working Group (IWG) response criteria (see [Appendix II](#)) after every two treatment cycles the first year, then every three cycles.

Investigators may choose to transition patients towards a stem cell transplantation (SCT) as appropriate after a response (CR, PR, mCR with HI, mCR without HI, HI) by the experimental or control treatment has been achieved. Patients who undergo SCT will be removed from study treatment and will be followed per the study calendar.

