9.3 Statistical Methods

9.3.1 Efficacy Analyses

Primary endpoint CR will be summarized for all randomized patients (ITT) as the proportion of patients (%) with CR. CR will be compared between treatment arms using a Cochran-Mantel-Haenszel (CMH) test stratified by age (< 65 years versus ≥ 65 years). In addition to presenting the CR rate and associated exact 95% CI for each treatment arm, the treatment effect will be described using the CMH estimate of the common odds ratio together with its associated 95% CI.

Duration of response (DOR) is defined as the time from the date when criteria for

response) are met to the date of relapse, progression, or death due to any cause, whichever occurs first. Patients alive without relapse or progression will have their DOR censored at the date of the last clinical assessment. The duration of CR will be summarized in each treatment arm by providing the median DOR together with associated 95% CI, using Kaplan-Meier methodology.

Overall response will be summarized in number (%) of patients in each category of responses (CR, PR, mCR with HI, mCR without HI, HI). ORR will be analyzed by using the similar method as primary endpoint CR. DOR, as defined above, will also be evaluated in regards to ORR.

Time to AML is calculated from first day of study treatment to first onset of AML. Kaplan-Meier methodology will be utilized. Rate of AML transformation will be analyzed by using the same method as primary endpoint CR.

Survival data are collected at treatment and follow-up periods. Patients will be followed until death. Overall Survival (OS) is defined as the number of days from the date of randomization to the date of death. Kaplan-Meier methodology will be utilized.

Relapse-free survival (RFS) is defined as the time from the date of randomization to disease relapse, progression or death from MDS, whichever occurs first. If neither event occurs, RFS will be censored at the date of the last assessment. Kaplan-Meier methodology will be utilized.

Time to AML, OS and RFS will be analyzed using the similar methods as DOR.

Transition rate to SCT will be analyzed using the similar methods as complete response rate.

Important subgroup analyses will be detailed in the Statistical Analysis Plan.

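### The rule for transplant before CR is not limited to the CR endpoint and, taken literally, conflicts with the ORR definition

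*Combined protocol and SAP*

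**What the plan says.** Section 8.2.3 (Stem Cell Transplant) adopts a treatment-policy approach. Transplanted patients stay in follow-up for survival and for relapse from whatever response they had, and those dates enter the analysis. The next sentence is the counting rule: "If for any reason a patient receives SCT prior to a documented CR they will not be counted as a response".

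Section 4.1 lets investigators move patients to transplant "as appropriate after a response (CR, PR, mCR with HI, mCR without HI, HI) by the experimental or control treatment has been achieved".

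The Synopsis, under secondary endpoints, states: "ORR is the proportion of patients achieving hematological improvement (HI), partial remission (PR), CR, marrow CR by the IWG 2006 criteria". Section 9.3.1 tabulates the same response categories and adds that "ORR will be analyzed by using the similar method as primary endpoint CR" and that "DOR, as defined above, will also be evaluated in regards to ORR". Neither place mentions an exclusion for transplant.

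**The concern.** The counting rule is triggered by the absence of a documented CR, but its consequence is loss of response status in general. In the transplant context, Section 4.1 uses the word response for five categories, four of which are not CR. The Synopsis (Duration of Follow-Up) and Section 7.6 define responders by the same list. With that meaning, a patient with a documented PR, marrow CR or HI who is transplanted before CR is scored as an ORR non-responder and has no response whose duration can be analysed.

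Two statisticians working from this text could therefore build different responder sets for ORR and for DOR. Section 9.3.1 makes this more likely, because an instruction to analyse ORR much as CR is analysed could be taken to carry the transplant rule across. The trial is open label, investigators decide when a patient moves to transplant, and transition to transplant is itself a compared secondary endpoint. The choice of reading is better fixed before data accumulate by arm.

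**Working it through.** **1. The plan's own figure.** Section 9.1 gives 77 per arm, CR 50% v 25%, two-sided alpha 0.05 and 90% power. The two-proportion formula with pooled variance under the null and no continuity correction is

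n = [1.960·√(2·p̄·(1−p̄)) + 1.2816·√(p1(1−p1) + p2(1−p2))]² / (p1−p2)², with p̄ = 0.375.

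This gives [1.960·√0.46875 + 1.2816·√0.4375]² / 0.0625 = 76.7, or 77 per arm, and power at 77 is 0.901. The figure reproduces. It concerns CR only and is the same under either reading of Section 8.2.3.

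**2. The texts side by side.**

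| Place | Patient with documented PR, marrow CR or HI, then SCT before CR |
|---|---|
| Section 4.1 | Had a response that permits SCT |
| Synopsis, secondary endpoints; Section 9.3.1 | Counts in ORR; DOR evaluated for ORR |
| Section 7.6 | Response assessments continue after SCT, monthly until relapse or death |
| Section 8.2.3, treatment-policy sentence | Followed for relapse from that response; date used |
| Section 8.2.3, counting rule | Not a response |

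The last row disagrees with the others. A patient cannot supply a relapse date for a response and also not have one.

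**3. Illustrative size.** The documents give no ORR and no rate of SCT before CR, so what follows rests on assumptions. Let a be the share of an arm that responds without CR, and s the fraction of those patients transplanted before CR.

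- ORR under the literal rule = ORR − a·s
- Patients reclassified per arm = 77·a·s
- Change in the ORR difference = −(a_E·s_E − a_C·s_C)

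Assume ORR 75% v 50%. With the planned CR rates of 50% v 25%, a = 25% in both arms. Power uses the same uncorrected two-proportion formula with 77 per arm.

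| s, experimental / control | Literal ORR | Patients reclassified | Difference | Power |
|---|---|---|---|---|
| 0 / 0 | 75 / 50% | 0 / 0 | 25 points | 0.901 |
| 10 / 10% | 72.5 / 47.5% | 1.9 / 1.9 | 25 points | 0.894 |
| 20 / 20% | 70 / 45% | 3.9 / 3.9 | 25 points | 0.888 |
| 40 / 40% | 65 / 40% | 7.7 / 7.7 | 25 points | 0.882 |
| 40 / 20% | 65 / 45% | 7.7 / 3.9 | 20 points | 0.707 |
| 20 / 40% | 70 / 40% | 3.9 / 7.7 | 30 points | 0.969 |

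The unchanged difference under equal s depends on a being equal in the two arms. If ORR were 70% v 50%, then a = 20% v 25%, and s = 40% in both arms gives 62% v 40%: the difference widens from 20 to 22 points. The direction therefore depends on quantities the documents do not give. If the rule is limited to CR, every row returns to the assumed 75 / 50%.

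**The case against.** The strongest reply is that context already limits the rule. Its trigger is a documented CR. Section 8.2 opens by naming CR and the time from CR to relapse as the primary endpoint, and the objectives call that endpoint the complete response rate, so the word response can stand for a complete one. Read this way, the rule stops a CR first reached after transplant from being credited to study treatment. ORR and DOR have their own definitions without a transplant exclusion, and the treatment-policy sentence together with Section 7.6 presupposes that non-CR responders keep their response after SCT. This stands as the more coherent reading and probably the intended one. It does not remove the defect, because no text available limits the rule to CR.

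A reader might infer more: that the plan means to drop these responders, or that the rule biases ORR against the experimental arm. For example, if 15% v 5% of each arm were transplanted from a non-CR response, 0.15 × 77 ≈ 12 against 0.05 × 77 ≈ 4 patients would be reclassified, a 10-point shift. The documents support neither inference. They give no such rates, and reversing them reverses the shift. Only patients transplanted before any CR are touched, and with planned CR rates of 50% v 25% experimental-arm responders may more often reach transplant after CR, where the rule does nothing. Nor does ORR's place at the head of the secondary list give it formal weight, since no testing hierarchy is stated.

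**Conclusion.** The wording of Section 8.2.3 conflicts with the ORR definition, with the list of responses after which SCT is allowed, and with the sentence before it. It should be corrected as an imprecise rule; it is not evidence of an intended exclusion. The consequence is confined to ORR and its DOR, and to non-CR responders transplanted before CR. The illustrated fall of 2.5–10 points in each arm's ORR rests on an assumed 25% of non-CR responders per arm and 10–40% of them transplanted. The effect on the between-arm difference may be nil or may go either way. The primary CR comparison and the sample size stand. Severity is minor.

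**What to change.** In Section 8.2.3, replace the end of the counting rule so that such a patient *will not be counted as a CR; any PR, marrow CR or HI documented before SCT still counts toward ORR and its DOR*. This reconciles the section with Section 4.1, the Synopsis endpoints and Section 9.3.1, and takes no position on when transplant should be given.

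The cost is one sentence. The CR rule, primary analysis and sample size do not change, and no new data are needed because Section 7.6 already collects response assessments after SCT.
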